This study will compare the HTD system with the two routinely used temperature measurement systems (tympanic and forehead) to understand the level of agreement that can be achieved and so its potential utility in triage and in a transportation and workplace setting. A secondary objective of this study are to assess if skin tone adds any additional differences

between a thermal camera based system temperature assessment and the routinely used tympanic and forehead based methods.

If results are encouraging the aim would then be to undertake a clinical investigation in order to get CE marking for use in a clinical setting.

100 staff and 100 patients will be consented with thermal images of their face taken as well as having their temperatures taken. The following measurements and information will be recorded:

- Forehead temperature from the HTD System
- Head temperature from the HTD System
- Tympanic temperature from a tympanic IR thermometer
- Forehead temperature from a forehead IR thermometer
- Age
- Ethnicity

A sample of size 100 will give 95% confidence intervals for the limits of agreement of +/- 0.34 standard deviations (<https://www-users.york.ac.uk/~mb55/meas/sizemeth.>). These limits of agreement will then allow determination of how close the temperature readings are between 1. Tympanic vs. HTD and 2. Forehead vs HTD and whether or not these are within +/- 0.2 degrees. It will demonstrate if there is a trend over the temperature range to understand consistency. The bias will be quantified using the mean difference (significance determined using a t-test).

The larger sample size (200) is proposed to gather a wider range of skin tone measures. Staff members will be recruited in addition to patients as this is likely to increase the diversity of the sample.

Although a BB source is not required for the new HTD system, a BB will be housed in the room where staff measurements are taken. Its inclusion gives another source of ground truth and will allow the calibration of all systems to be checked at regular intervals throughout the study.

3. Research Questions

Primary

- To determine the diagnostic accuracy of HTD for the measurement of fever, using an equivalence comparison with the maximum temperature recorded with two routinely used temperature measurements (tympanic and forehead), margin $\pm 0.2^{\circ}\text{C}$.

Secondary

- To determine if skin tone is an independent confounding factor in the measurement of fever using HTD

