All the information obtained about participants in the course of the study is confidential and will be held in accordance with the General Data Protection Regulation (GDPR 2018). Data will be entered into a custom graphical user interface (GUI). Once the images and metadata have been recorded they will be regularly and periodically encrypted and then the unencrypted images deleted from the device automatically. Encrypted data will be synced with an encrypted dropbox and then transferred to Thales secure servers. Data will be unencrypted when it reaches the secure Thales servers.

Data are stored on dedicated storage area implementing Mandatory Access Control for an explicit list of authorised users. The management of those IT resources are performed by Thales UK Ltd. Thales UK Ltd is certified against the Cyber Essential Plus scheme.

Data Analysis

Personal data will be collected and processed only for the purpose of answering the research questions. The thermal images are Personally Identifiable Information (PII) and will be retained by the company for as short a time as possible before being permanently deleted. The other data items are not PII and are low risk in terms of identifying the patient from anonymised data. Personal information will not be shared with anybody outside the study.

The feasibility study data will primarily be analysed using statistical methods looking for relationships between facial feature temperatures and patient metadata. Artificial Intelligence (AI) /Convolutional Neural Network (CNN) based feature detection algorithms *may* be used to find the coordinates of the key points on the face in the visible image. The corresponding coordinates can be found with fine camera alignment and calibration. The thermal features may then be extracted for analysis along with the patient metadata. A manual feature extraction method may be used instead of the AI/CCN method if deemed more efficient for the smaller, initial dataset of 200 patients. Manual inspection of thermal images will be used to look for patterns and anomalies.

Three readings will be done per participant and comparisons done between:-

1. Tympanic vs. Thermal
2. IR vs. Thermal

A sample of size 100 will give 95% CIs for the limits of agreement of +/- 0.34 standard deviations (i.e. about a third of the standard deviation)

A sample of size 200 will give 95% CIs for the limits of agreement of +/- 0.24 standard deviations (i.e. about a quarter of the standard deviation)

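### The primary equivalence question does not adopt the limits-of-agreement criterion or the comparators of the Aims, and the t-test on the mean difference cannot settle the ±0.2 °C margin

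*Protocol*

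**What the plan says.** - Protocol, section 3 (Research Questions, Primary): the accuracy of HTD is to be determined "using an equivalence comparison with the maximum temperature recorded with two routinely used temperature measurements (tympanic and forehead), margin" ±0.2 °C. The comparator is a single value, the larger of two readings. The question does not say whether the mean difference, the limits of agreement or the individual differences must lie inside the margin.
- Protocol, section 2 (Aims): "These limits of agreement will then allow determination of how close the temperature readings are between" tympanic and HTD, and forehead and HTD, and "whether or not these are within +/- 0.2 degrees". Here the limits of agreement are the instrument, and there are two separate comparisons.
- Protocol, section 2, next but one sentence: "The bias will be quantified using the mean difference (significance determined using a t-test". This is the only significance test in the protocol.
- Protocol, section 6 (Data Analysis): the two pairwise comparisons are repeated with the precision statement "A sample of size 100 will give 95% CIs for the limits of agreement of +/- 0.34 standard deviations", and 0.24 SD for 200. No rule against ±0.2 °C is given there.
- Protocol, section 2: "If results are encouraging the aim would then be to undertake a clinical investigation", with CE marking as the goal.

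**The concern.** An equivalence question with a numerical margin needs one named quantity, one comparator and an inference that refers to the margin. Here these are spread over two sections that do not match.

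A t-test of the mean difference ordinarily tests zero. A non-significant result does not show that the difference is within ±0.2 °C, and a significant one does not show that it is outside.

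The choice of quantity also matters. The criteria are nested: if both limits of agreement lie within ±0.2, so does the 90% CI of the mean, because 1.96 SD is far larger than 1.653 SD/√200. The reverse fails. Any ambiguity therefore works in one direction: the mean can meet the margin while the limits miss it. A next step that depends on encouraging results is better served if the deciding quantity is fixed beforehand.

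**Working it through.** **Inputs.** Margin ±0.2 °C (section 3). n=200, from "100 staff and 100 patients will be consented with thermal images of their face taken", and n=100, which the protocol also uses for precision. Precision formula 1.96·√(3/n) in SD units (section 6). The protocol text gives no SD of paired differences, so every SD below is an assumption. Differences are taken as normal, one per participant.

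**Step 1: the protocol's own figure.** 1.96·√(3/100) = 0.3395 and 1.96·√(3/200) = 0.2400. The stated 0.34 and 0.24 reproduce. The fuller formula 1.96·√(1/n + 1.96²/(2(n−1))) gives 0.336 and 0.237.

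**Step 2: the t-test and the margin.** Take a true bias of 0.10 °C, inside the margin. The t-test is two-sided at 5% (noncentral t). Equivalence of the mean is the 90% CI lying within ±0.2.

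| n | SD (°C) | t-test significant | 90% CI within ±0.2 |
|---|---|---|---|
| 200 | 0.3 | 99.7% | 99.9% |
| 200 | 0.4 | 94% | 97% |
| 200 | 0.5 | 80% | 88% |
| 100 | 0.3 | 91% | 95% |
| 100 | 0.4 | 70% | 80% |
| 100 | 0.5 | 51% | 63% |

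So the test is often significant although the mean is equivalent. Conversely, with n=200, a deliberately extreme SD of 1.5 °C and a true bias of 0.25 °C (outside the margin), it is non-significant in about 35% of studies, while the 90% CI would show equivalence in about 1%.

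**Step 3: largest SD that each criterion tolerates at zero bias.**

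- Mean, 90% power: approximately 0.2·√n/(1.645 + 1.645), which is 0.608 (n=100) and 0.860 (n=200). With the t distribution it is 0.604 and 0.857.
- Point limits of agreement: 0.2/1.96 = 0.102.
- Outer 95% bounds of the limits: 0.2/(1.96 + 1.96·√(3/n)), which is 0.2/2.2995 = 0.087 (n=100) and 0.2/2.2000 = 0.091 (n=200).

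The ceilings for the limits are values at which they just fit. To pass with high probability the true SD would have to be lower still.

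**Step 4: the gap at an assumed SD of 0.4 °C.** At zero bias the mean passes in at least 99.9% of studies at either n. The limits are ±1.96·0.4 = ±0.78 °C, and the share of individual differences within ±0.2 is 2Φ(0.2/0.4) − 1 = 38% (50% at SD 0.3, 31% at SD 0.5).

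**Step 5: one data set.** n=200, mean 0.10, SD 0.4: SE = 0.4/√200 = 0.0283; t = 3.54, p = 0.0005; 90% CI 0.10 ± 1.653·0.0283 = 0.05 to 0.15; limits 0.10 ± 0.784 = −0.68 to 0.88. The t-test finds bias, the mean is within the margin, and the limits are far outside it.

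**The case against.** Three stronger readings are tempting, and the documents support none of them.

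- *That the protocol attaches no quantity to ±0.2.* It does: the Aims apply the margin through limits of agreement, the sample size rests on their precision alone, and no sentence ties the mean difference to ±0.2. It is natural to carry that criterion over to the primary question. What stands against this is that the primary question does not say so and compares HTD with the maximum of the two readings, so even a reader who carries it over cannot tell which limits are meant.
- *That the t-test is the planned test of equivalence.* The protocol gives it one job, describing bias, which is a usual companion to limits of agreement. The fault is narrower: it is the only inference stated for the mean, and it does not address the margin.
- *That a passing mean will be reported as success.* Nothing says so. The data are described as coming from a feasibility study, and the remark about encouraging results is not a formal decision rule. The ambiguity allows such a report; it does not plan it.

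Two further points are fair. Detail such as the confidence level may stand in an SAP that is not shown, and its absence is not the finding; the mismatch between two sections of the protocol is. The figures also rest on assumed SDs and on one difference per participant. Section 6 mentions three readings per participant without saying whether they are replicates or one per device, and replicates would change the relevant SD.

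**Conclusion.** The point holds in a limited form. The Aims contain a coherent criterion, but the primary question neither adopts it nor uses the same comparators, and a significance test of the mean difference cannot support or refute equivalence within ±0.2 °C.

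The practical size depends on an SD that the protocol does not give. Under the assumptions above, the mean tolerates an SD about six (n=100) to eight (n=200) times that tolerated by the point limits. At zero bias and n=200, any SD between about 0.10 and 0.86 °C would typically give opposite answers. The logical gap does not depend on the SD. Severity is minor to moderate.

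**What to change.** 1. In the Aims, report the mean difference with a 90% CI judged against ±0.2 °C (equivalent to two one-sided 5% tests) in place of relying on t-test significance. The t-test may stay as a description of bias only.
2. In the primary question, state that the limits of agreement, with the outer bounds of their 95% CIs, are the criterion judged against ±0.2 °C, and that a passing mean alone will not be reported as agreement.
3. State which comparator applies, the maximum of the two readings or each thermometer separately, so that sections 2, 3 and 6 match.

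This costs a few sentences and no extra participants or measurements. The downside is that the sponsor commits in advance to a stricter result: at zero bias the outer bounds fail at any SD of differences above about 0.091 °C (n=200) or 0.087 °C (n=100).

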- To establish performance of internal calibration of Thales device
- To power for a definitive Clinical Investigation to determine clinical efficacy and safety cut off with HTD

4. Study Design

Patient Identification

Two groups will be identified

1. Patients who present to the Emergency Department (ED) in QEUH will be approached either by ED nurses or clinical fellows they can approach reception staff/nurse directly for information after reading posters on the ED wall.
2. QEUH ED staff will be approached either by ED nurses or clinical fellow.

Inclusion criteria

- *Patients ≥ 16 years old with no upper age limit*
- *Patients able to read and understand English*
- *Patients able to give informed consent*
- *Patients being triaged through ED for any complaint (not necessarily COVID-19)*
- *QEUH ED staff*

Exclusion criteria

- *Patients not meeting the inclusion criteria*
- *Patients who do not have capacity to consent*
- *Patients attending ED who are fast-tracked without triage*

Consent

Participants will be given a participant information sheet (PIS v2) to read while they are in waiting to be triaged (patients) or working in the ED (staff). There will be posters displayed publicising the study, and if people are interested they can ask reception staff or a nurse for more information. The nurse or fellow will go through the PIS and provide opportunity to ask questions. Due to the circumstances there is no opportunity for patients to take the PIS away and discuss it with friends/family which would be preferred. If the patient/staff member wishes to participate, a consent form will be provided which has some statements to agree to and sign. The participant can keep a copy of the signed consent form as well as the PIS. Failure to consent will not change clinical care for patients.

The PIS will make it clear that Thales will hold a copy of the identifiable images for a maximum of 1 year. Thales will securely store and analyse visible and thermal data required for future algorithm upgrades. It is anticipated that Thales will require to hold onto both visible and thermal data long enough to be required for regulatory purposes. For example, it is anticipated that the thermal data, and associated metadata, will be required for a maximum of ten years and the visible data for a maximum of one year, after which time the data will be securely destroyed.

Study procedures

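### The primary question promises diagnostic accuracy for fever, but the method, analyses, precision basis and recruitment support only an agreement conclusion over the temperatures observed

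*Protocol*

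**What the plan says.** Section 3 of the protocol states the primary question as "To determine the diagnostic accuracy of HTD for the measurement of fever, using an equivalence comparison with the maximum temperature recorded" with the tympanic and forehead methods, margin ±0.2 °C. A secondary question uses the same fever wording: "To determine if skin tone is an independent confounding factor in the measurement of fever using HTD".

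The rest of the protocol describes an agreement study:

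- **Aim (section 2):** "to understand the level of agreement that can be achieved" between HTD and the two routine methods.
- **Accuracy analyses (section 2):** limits of agreement for tympanic vs HTD and forehead vs HTD, judged against ±0.2 degrees; a mean difference with a t-test; and a look at trend, of which the protocol says "It will demonstrate if there is a trend over the temperature range to understand consistency".
- **Other analysis (section 6, Data Analysis):** "The feasibility study data will primarily be analysed using statistical methods looking for relationships between facial feature temperatures and patient metadata". This is not an analysis of fever accuracy either.
- **Sample-size basis (sections 2 and 6):** the width of the confidence interval for the limits of agreement. The increase to 200 is justified by the range of skin tone.
- **Recruitment (sections 2 and 4):** 100 staff and 100 patients. On staff: "Staff members will be recruited in addition to patients as this is likely to increase the diversity of the sample". Patients are eligible if they are triaged in the emergency department with any complaint. History of fever is recorded (section 4, Study procedures) but selects no one.
- **Later work:** a secondary objective is "To power for a definitive Clinical Investigation to determine clinical efficacy and safety cut off with HTD", and section 10 places a fever yes/no result in the clinical investigation that would follow encouraging results.

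**The concern.** Diagnostic accuracy for fever means how well a device separates febrile from afebrile people. That needs a reference definition of fever, a measure such as sensitivity and specificity, and enough febrile people to estimate it. The primary question names this target but attaches a method that measures the size of a temperature difference.

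If the wording stays, an equivalence result that may rest on few febrile readings stands as the formal answer to a question about fever. Agreement at the temperatures sampled says little about agreement in a febrile range that is hardly sampled. The trend analysis would help there, but it depends on the same cases being present. The result is meant to inform use in triage, transport and workplaces, where detecting fever is what matters, so readers are likely to take the primary question at its word.

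The statistical analysis plan is not at hand. It could add a threshold and accuracy measures, but it could not supply febrile participants whom recruitment does not secure.

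**Working it through.** **1. The protocol's own precision figures.** Section 6 gives 1.96 × √(3/n) as the multiplier of the SD.

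- n=100: 1.96 × √0.03 = 0.339, stated as 0.34.
- n=200: 1.96 × √0.015 = 0.240, stated as 0.24.

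Both reproduce. They describe the precision of the limits of agreement. The protocol gives no fever proportion, fever threshold or target sensitivity, so no precision for fever classification can be derived from it. Every input in steps 2 to 4 is an assumption.

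**2. How many febrile participants?** Take staff as afebrile and let a proportion p of the 100 patients be febrile. The expected number is 100p, and the chance of none is (1−p)^100.

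| p | Expected febrile | Chance of none |
|---|---|---|
| 1% | 1 | 0.99^100 = 37% |
| 2% | 2 | 0.98^100 = 13% |
| 5% | 5 | 0.95^100 = 0.6% |
| 10% | 10 | 0.90^100 = 0.003% |

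**3. How precise would sensitivity be?** Exact (Clopper-Pearson) 95% intervals:

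| Detected / febrile | 95% interval |
|---|---|
| 5/5 | 48% to 100% |
| 9/10 | 55% to 99.7% |
| 18/20 | 68% to 99% |

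**4. Does agreement within ±0.2 °C settle classification?** Let the reference temperature be T ~ N(36.8, s²), the difference (HTD minus reference) be D ~ N(0, d²), independent of T, and the cut-off be c. Sensitivity is P(T + D ≥ c | T ≥ c), found by numerical integration. The cut-offs are illustrative only.

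| s, c (implied febrile share) | d=0.10 | d=0.20 | d=0.30 | d=0.50 |
|---|---|---|---|---|
| 0.5, 38 (0.8%) | 84% | 74% | 68% | 62% |
| 0.5, 37.5 (8%) | 88% | 79% | 73% | 66% |
| 0.7, 38 (4%) | 90% | 82% | 76% | 69% |
| 0.7, 37.5 (16%) | 92% | 86% | 80% | 73% |
| Limits of agreement, ±1.96d | ±0.20 | ±0.39 | ±0.59 | ±0.98 |

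With zero bias, two one-sided 5% tests of the mean against ±0.2 °C at n=100 pass with probability of about 98% at d=0.50, and more at smaller d. The last row shows that only d=0.10 also keeps the limits of agreement within ±0.2 °C (1.96 × 0.10 = 0.196).

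**The case against.** The strongest reply is that the protocol already limits its claim. The same sentence fixes the method and margin, the aims speak of agreement, the cut-off and yes/no result are deferred, and section 10 calls the results preliminary. No section commits to reporting sensitivity, specificity or a fever classification. This stands as a description of intent, and it is why the point is one of wording and scope. It also confirms the mismatch: the protocol treats fever classification as later work while naming it as the present primary question.

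Two stronger readings are tempting, and the documents do not support them.

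- **That there will be no febrile participants.** The patients are emergency department attenders at triage and will probably include some. At an assumed 5% to 10%, the chance of none is 0.6% or less. What holds is that the number is left to chance.
- **That a device with sensitivity of 62% to 86% (SD of differences 0.2 to 0.5 °C) would be judged satisfactory.** It could pass a test of mean equivalence. But section 2 also judges the limits of agreement against ±0.2 degrees, and limits of ±0.39 to ±0.98 °C fail that. The lowest figures also come from a setting with only 0.8% febrile, where the modelled febrile readings lie close to the cut-off.

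**Conclusion.** The point holds as a mismatch between the primary question and everything that serves it: method, analyses, precision basis and recruitment. The study can support an agreement conclusion over the temperatures observed. It cannot support a conclusion on fever classification.

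The mismatch rests on the protocol's text alone and is firm. Its size rests on assumed inputs. With 5 to 20 febrile patients, sensitivity would be known only to within wide intervals, with lower bounds of 48% to 68% in the examples shown. Even a device with zero bias whose limits of agreement just fit ±0.2 °C has modelled sensitivity of 84% to 92%, so meeting the margin does not by itself answer the fever question. The agreement study remains sound; its headline claim should be changed.

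**What to change.** 1. Reword the primary question as agreement or equivalence of HTD temperature with the routine thermometers, margin ±0.2 °C, and remove the reference to diagnostic accuracy for fever.
2. Reconcile the comparator in the same edit. The question uses the maximum of the two routine readings, whereas sections 2 and 6 compare HTD with tympanic and forehead readings separately.
3. In the skin-tone question, refer to the measurement of temperature instead of fever.
4. State that the conclusion applies only to the temperature range observed, and report how many participants were in the febrile range at a threshold the sponsor fixes in advance.
5. Label any sensitivity or specificity as exploratory input to the definitive investigation.

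The cost is wording changes to two questions, one statement of scope and one reported count, with no new participants, procedures or sample size. The downside is a more modest primary claim, with fever performance left open until the definitive study. Keeping the fever claim instead would need a reference definition of fever, accuracy measures and a planned number of febrile participants, which is a different design.

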In a pilot study conducted in the Emergency Department, Queen Elizabeth University Hospital (20/NS/0064), the Thales High Temperature Detection (HTD) system was found to be more accurate than a tympanic thermometer (Ref) which captures Infrared radiation emitted by the tympanic membrane in the ear. (Figure 1) or forehead thermometer. Tympanic temperature measurements are typically used in the hospital setting in Scotland whereas forehead IR measurement is common in transportation and workplace settings.

[figure not shown]

Figure 1: Distribution of variance between measurements for each subject for tympanic thermometer and HTD (n = 80)

The HTD has been redesigned in response to three key findings from the pilot study:

- The relative temperature of some facial features correlated more strongly with tympanic temperature than others.
- Having an external Black Body (BB) calibration source in the scene at all times was impractical in a clinical environment
- Camera systems require to be compact and portable to be useful to clinical staff.

As a result, the HTD is now significantly reduced in size, including peripheral devices. A novel calibration solution has been designed (and patented) that not only removes the need for the black body source but allows for a more accurate temperature evaluation. In addition, facial feature detection has been integrated into the software to allow it to automatically locate the patient's head and in the near future, automatically determine the temperatures of individual facial features. This development will capture facial feature detection – not facial recognition.

[figure not shown]

Figure 2: Temperature Measurement vs Actual

Figure 2 shows that the thermometer (juniper) in forehead mode appeared to return measured temperature + an offset to estimate core. The HTD can be calibrated in the same way i.e. to use the actual forehead temperature returned from the HTD plus the same offset. For tympanic comparison, the maximum temperature returned by the HTD (probably the canthus) correlates best – but it is still likely that some post processing will be required to ensure that a direct comparison can be made.

2. Aims

The Thales HTD (High Temperature Detection) System is a thermal camera based, human temperature measurement system.

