After the participant has consented to take part, the research will take a front view with the thermal imaging camera. The following data is routinely collected at triage and a copy of the data will also be entered into the Thales electronic Case Report Form (eCRF). No patient name or personal details will be held by Thales.

- Temperature
 - Oral
 - IR Forehead
 - Ear
- History of Fever Y/N
- Age
- Ethnicity
- If they are wearing contact lenses

While desirable to have uncovered face thermal images, it is accepted that some patients may choose to wear facemasks. Patients will be asked to remove spectacles.

It is expected that the thermal imaging system will sit on a table or worktop and image patients approximately 1.5m to 2.0m away. The system will require access to a mains wall socket. The kit will remain set up in a locked room when not being used.

The system will comprise of:

- Surface Pro Tablet PC;
- Thales camera mounted on a portable tripod;
- Thermal calibration Black Body source (for calibration validation purposes only).
- MiFi internet connection
- Forehead thermometer
- Tympanic thermometer

The tablet will auto-run easy to use software allowing hospital staff to record:

- Thermal and TV image of the patient front on;
- Non-personal patient metadata:
- Patient temperature measured by existing clinical methods

The system will be simple to use and aims to minimise the disruption of the QEUH staff. Thales will have provided training of QEUH staff on how to operate the equipment and support of the equipment during the data collection activity. Training will take the form of a pdf, training video and if required a video conference call.

Follow Up

There is no follow up required – patients are only required to commit to one hospital visit when they initially present at ED and have their picture taken with the thermal imaging camera. Staff will require only to have their picture taken.

5. Withdrawal

If participants wish to withdraw their consent after the intervention (after the image has been taken) they can do so and it will not affect their clinical treatment. They may withdraw from the study at their own request and are not required to give a reason for this. They will be made aware that this will not affect their future care. Participants will be made aware that should they withdraw the data collected to date will be retained and used in the final analysis.

6. Data handling, analysis and archival

Data Handling

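### The protocol is inconsistent on where patient reference temperatures come from and sets no limit on the interval between reading and thermal image

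*Protocol*

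**What the plan says.** The only procedural text on how patient temperatures reach the dataset is in Section 4, Study procedures. First comes the image: "After the participant has consented to take part, the research will take a front view with the thermal imaging camera". Then come the temperatures, listed as oral, IR forehead and ear: "The following data is routinely collected at triage and a copy of the data will also be entered" in the electronic case report form. The same section has the tablet record a temperature obtained by existing clinical methods. No interval between image and temperature is given, nor their order. Under Consent, patients read the information sheet while waiting for triage.

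Other parts point elsewhere:
- Section 2 (Aims) says that 100 staff and 100 patients will be imaged and have their temperatures taken, and lists a tympanic and a forehead IR reading for recording.
- Section 6 (Data Analysis) promises three readings per participant, without saying which three, with which device or when.
- The Section 4 equipment list includes a forehead and a tympanic thermometer, but no step says who uses them, on whom or when.
- The background text gives tympanic measurement as the usual method in Scottish hospitals and says that "forehead IR measurement is common in transportation and workplace settings".
- Staff are not triaged, so there is no triage record to copy for them.

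**The concern.** An agreement study attributes the whole within-person difference to the two methods. That holds only if both measure the same temperature at effectively the same time. If a patient's reference is a triage value and the image is taken at some other point in the visit, any real change in between enters the difference and is counted against the HTD. Without paired times, no later analysis can separate the two.

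Two further matters follow from the same ambiguity. Patients and staff may obtain their references by different routes and then be pooled. And the primary question in Section 3 uses the maximum of the tympanic and forehead readings, so both are needed for every participant. The background gives reason to ask whether a triage record would hold the forehead value.

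**Working it through.** **Inputs from the protocol.** Margin ±0.2 °C (Sections 2 and 3); 100 patients and 100 staff (Section 2); half-width of the 95% CI for a limit of agreement, 1.96·√(3/n) in SD units (Section 6).

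**Assumptions.** The protocol gives no SD of differences and no gap. I write s for the SD of differences with simultaneous readings and g for the SD of real temperature change between reading and image. I take zero bias, and g independent of s with mean zero. The values of s and g are illustrative.

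**1. The plan's own figures.**
- n=100: 1.96·√(3/100) = 0.339, stated as 0.34.
- n=200: 1.96·√(3/200) = 0.240, stated as 0.24.

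Both reproduce. They are in SD units, so a time gap leaves them unchanged; it widens the limits and their intervals in °C.

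**2. The SD that the margin tolerates.**
- Limits inside ±0.2: 0.2/1.96 = 0.102 °C.
- Limits and their n=200 confidence bounds inside: 0.2/(1.96 + 0.240) = 0.091 °C.

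A gap SD of 0.1 °C would leave √(0.102² − 0.1²) ≈ 0.02 °C for both devices together under the first criterion, and nothing under the second.

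**3. Effect of a gap on the limits.** In an analysis of patients alone the limits are ±1.96·√(s² + g²). If staff have no gap and form half the sample, the pooled limits are ±1.96·√(s² + 0.5g²).

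| s (°C) | g (°C) | Patients only | Pooled, gap in patients only |
|---|---|---|---|
| 0.1 | 0 | ±0.196 | ±0.196 |
| 0.1 | 0.1 | ±0.277 | ±0.240 |
| 0.2 | 0 | ±0.392 | ±0.392 |
| 0.2 | 0.1 | ±0.438 | ±0.416 |
| 0.2 | 0.2 | ±0.554 | ±0.480 |
| 0.2 | 0.3 | ±0.707 | ±0.571 |
| 0.3 | 0 | ±0.588 | ±0.588 |
| 0.3 | 0.3 | ±0.832 | ±0.720 |

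With s = 0.1 °C a gap SD of 0.1 °C moves the limits from just inside the margin to outside it, even when only patients are affected. With s = 0.2 °C or more the limits already fail without a gap. There the gap changes the estimate of how well the device agrees, not the pass or fail result.

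**The case against.** The strongest reply is that the study readings are already intended. The Aims say that participants have their temperatures taken, Data Analysis promises readings per participant, both thermometers are in the kit, and staff values can hardly come from triage. Patients are approached while waiting for triage, there is one visit, and the same tablet records image and temperature, so near-simultaneous capture fits the text. This stands as far as it goes: a reader might infer that the kit thermometers are not used for patients, or that a long gap is planned, and the documents establish neither. It does not remove the copying sentence, which is the only stated procedure, or supply the missing interval.

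Three other stronger readings are also unsupported:
- That triage devices escape the black-body check. Section 2 places the black body where staff are measured but says that it serves to check all systems, and no triage device is described.
- That the forehead comparison will be lost. The background statement is general, while Section 4 names IR forehead among the triage data. The two fit poorly, but this does not predict missing values.
- That the whole sample carries the gap. Only patients have triage readings, so the patient-only column does not describe the pooled result.

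Finally, if equivalence were judged on the mean difference, random gap noise would matter little. At n=200 and s = 0.2 °C the 95% half-width is 1.96·0.2/√200 = 0.028 °C, and 0.050 °C even with g = 0.3 °C in everyone. But Section 2 sets the limits of agreement against ±0.2, and a systematic change between triage and imaging would shift the mean as well.

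**Conclusion.** The point holds as an inconsistency in the measurement procedure that should be settled before data are collected. The protocol does not make clear which device supplies the patient reference, and it leaves the interval to the image open. Followed as written, the copying rule can put real temperature change into a comparison with room for a total SD of only about 0.10 °C (0.091 °C with the n=200 bounds inside).

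The size of the effect in this trial is unknown. The illustration from s = 0.2 °C, with pooled limits rising from ±0.39 to between ±0.42 and ±0.57 °C and patient-only limits to between ±0.44 and ±0.71 °C, rests on assumed SDs, zero bias and a gap in patients only. It is a risk to remove, not a demonstrated loss.

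**What to change.** Reconcile the background, Section 2, Section 4 (Study procedures) and Section 6 (Data Analysis) so that they say one thing:
- For patients and staff alike, the tympanic and forehead reference readings are taken with the kit thermometers in the same sitting as the image, within a few minutes, with each reading and the image time-stamped on the tablet.
- These are the values analysed. State what the three readings per participant are.
- The triage temperature is kept as a descriptive variable only.

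The cost is a protocol amendment, about a minute per participant, and up to two extra brief non-invasive readings per patient. Both thermometers are already listed, so no new equipment is needed. If the sponsor already intends this, the amendment only makes it explicit.
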